
Specific Objectives:

Develop and test the feasibility of the "Connect" intervention for increasing PA affect, cognition, and MVPA of underserved youth within ASPs. The effects of the intervention on youth body mass index (BMI) trajectories will also be explored and will have implications for impacting BMI as the targeted outcome of a larger R01 trial.

Primary Aims (Program Development and Feasibility):

1. Through qualitative interviews with staff and youth at ASP sites serving at-risk youth assess:
a) conceptual constructs most relevant for facilitating and supporting youth PA social goals; b)

barriers present within ASPs for meeting PA social goals (addressed in Phase 1, previously approved by IRB: Pro00031648).

2. Explore the feasibility of the Connect program. The Connect program will be documented to be feasible as shown by: 1) youth's greater perceived connectedness and PA affiliation goal orientation from baseline to post-intervention; 2). changes in targeted social climate components from baseline to post-intervention as measured by systematic observations, 3) staff perceptions of feasibility and acceptability of program as measured by a baseline and follow-up readiness assessment, and; 4) adequate dose and fidelity of program implementation as indicated by weekly process evaluations.

Secondary Aims (Document the preliminary impact of the Connect program on PA outcomes):

1. Assess whether youth in the social climate program (vs. comparison) demonstrate greater increases in positive PA affect, cognitions, and MVPA from baseline to 12-weeks post-intervention.
2. Explore whether youth in the social climate program (vs. comparison) demonstrate healthier BMI trajectories (e.g., slight reduction) from baseline to 12-weeks post-intervention.
3. Assess whether changes in targeted social mechanisms will mediate the effects of the intervention on changes in PA affect, cognitions, and MVPA from baseline to post-intervention.

C. Background and Significance

Physical Activity for the Prevention of Obesity and Related Disease

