Targeted Population, Recruitment, and Retention. We aim to recruit 8 middle-school ASPs located within a 70 mile radius of Columbia that serve a primarily underserved population of middle school youth (6th-8th grade) youth. All ASP sites will need to include 1 hour of daily PA/freeplay as one component of the curriculum and be similar in size, percentage of youth per site on free or reduced lunch, race, and gender. One ASP will be asked to participate in the pilot during year 1 and will be compared to a school-based control (youth in the control will receive our general health curriculum administered in their health class during the school day). During year 2, six ASPs will be randomized to the treatment or control (general health curriculum) conditions after baseline data collection. ASP staff and all youth enrolled in the program will be asked to participate in the study. To be eligible, youth must 1) be enrolled in the ASP, 2) have parental consent and assent to participate, and 3) be available for baseline and post-intervention measurement. Youth will be excluded from participation only if they have a medical condition that would interfere with the program's prescribed PA.

Overview of Intervention.

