Task and Ego Orientation in Sport Questionnaire (TEOSQ) assesses youth task (mastery) or ego (performance) orientations towards PA and is predictive of value, intrinsic interest and enjoyment in PA (reliability coefficients range from .71 to .87)⁷⁸. **The Need for Relatedness Scale**⁷⁹ will assess feelings of social connections to others within the ASP setting and has been previously validated using other SDT constructs⁸⁰⁻⁸² (reliability coefficients range from .86 to .92; 5-pt scale, $M=3.74$; $SD=.75$). The **Perceived teacher support scale**⁸³⁻⁸⁵ (reliability coefficient =.84; 5-pt scale, $M=3.22$; $SD=1.05$) and **The Peer Motivational Climate in Youth Sport Questionnaire**⁸⁶ (reliability coefficients range from .69 to .82; 7-pt scale, $M=3.18$, $SD=1.32$) will be used to measure youth perceptions of staff and peer connections. Validity of both measures has been supported in previous work and shown to correlate with PA enjoyment, effort, and prosocial and social responsibility goals.⁸³⁻⁸⁶ **The Social Support and Exercise Survey** will measure changes in youth family and friend social support for youth PA.⁸⁷ (See Appendix G for Youth Survey Measures).

Secondary Aims 1, 2, and 3: Youth MVPA, Cognitions, Affect, and BMI

Youth Physical Activity (Accelerometer). Objective assessments of PA will be obtained on youth with omni-directional accelerometers (Acticals; Mini-Mitter, Bend, OR).⁸⁸ Actical has demonstrated correlations between activity counts and energy expenditure of individuals measured concurrently with accelerometers (e.g., MTI Actigraph, Caltrac, Tritrac) in several studies.⁸⁹ Youth will wear an accelerometer over 7 consecutive days to calculate PA at baseline, endpoint, and post-intervention. Data will be recorded in 30-s epochs to best capture short bouts of vigorous activity,^{90,91} and raw activity data will be converted into time spent in moderate (3-5.9 METS), vigorous (6-8.9 METS), and MVPA (3-8.9 METS) based on activity count thresholds for children identified by Puyau et al.⁸⁸ [name] (PI) and [name] (Co-I) have been involved in multiple trials using accelerometer to measure PA in youth.²⁵⁻²⁷

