Primary Aim 2. The second primary aim of the study is to assess whether youth in the intervention demonstrate greater change in the 3 PA social affiliation mechanisms from baseline to post-intervention. Gains in these social mechanisms will be assessed with repeated measures ANCOVA models in which time (baseline to end of program and baseline to post-intervention) is a within subject factor and treatment is a between subjects factor for social mechanism variables measured in both conditions. Analyses will control for demographics, baseline BMI, and any other variables for which there are baseline differences between treatment and control groups (e.g., PYD, depression). To examine overall changes in social mechanisms within the intervention alone, similar repeated measures ANCOVAs will be used, with the between subjects treatment factor dropped. The test of interest will be the within subjects factor of time, with affiliation goals expected to improve over time. Process Evaluation, used to assess the quantity (dose) and quality (fidelity) of program implementation, will also serve as feasibility assessments. Our group has extensive experience with “dose-response” analyses.²⁷ Weekly observational assessments of program facilitation, using standardized ratings developed for other studies,¹⁰¹⁻¹⁰³ will be reduced to a total score, indicating overall fidelity to the activity observed.

Secondary Aims. **Secondary Aims 1 and 2** tests the a-priori hypothesis that youth in the intervention (vs. comparison) will have greater improvements in PA affect, cognitions, and MVPA and healthier BMI (z-score) trajectories (e.g., slight reduction; less increase) from baseline to post-intervention. This study will also provide us with information on the effect size that might be expected to power an efficacy trial after completion of the R21 project. Greater improvements will be assessed with several repeated measures ANCOVA models in which time (baseline to post-) is a within subject factor and treatment is a between subjects factor for PA variables measured in both conditions. Analyses will control for demographics (and BMI for PA outcomes) and other variables for which there are baseline differences between treatment and control groups. Multiple imputation protocols^{104,105} will be used to address missing accelerometer data (see our previous work).²⁵

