Secondary Aim 3 explores whether changes in youth PA social orientations mediate the effect of the intervention on changes in adolescent PA outcomes. This hypothesis will be tested with a

multiple mediator model (estimated path model) where the indirect effect of the program on PA through social mechanisms will be examined. Bootstrapped estimates of the mediated effect will be examined in line with recommendations from methodological research.^{106,107} Both the total indirect effect of all variables together and specific mediated effects of each variable will be examined.

F. Human Subjects

Protection of Human Subjects

Risks to the Subjects

Human Subjects involvement and Characteristics. Subjects will be healthy male and female adolescents and adults. To be eligible, adolescents must 1) be currently enrolled in the afterschool program, 2) have parental consent to participate, and 3) agree to study participation and random assignment, and 4) be available for baseline and post-intervention measurement. Adolescents will be excluded from participation if 1) have a medical condition that would interfere with the prescribed physical activity intervention plan, 2) are developmentally delayed such that the intervention materials will not be appropriate or, 3) are in treatment for a psychiatric disorder. To be eligible, adults must 1) be part of the afterschool staff, 2) have no medical condition or disorder that would limit participation, 3) be available and able to participate in the interviews and/or the intervention phase for the study period.

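### The Secondary Aim 3 mediation model ignores the randomised afterschool program, so its bootstrap intervals are too narrow when sites differ; over one shared interval it also cannot establish direction

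*Combined protocol and SAP*

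**What the plan says.** **Model.** Secondary Aim 3 in section E (Analysis Plan) "explores whether changes in youth PA social orientations mediate the effect of the intervention on changes in adolescent PA outcomes". It uses a path model with several mediators and bootstrapped estimates. "Both the total indirect effect of all variables together and specific mediated effects of each variable will be examined". That paragraph gives no ASP term, unit of resampling, measurement wave, lag or reverse-order model.

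**Unit of randomisation.** Section D, Targeted Population, says "six ASPs will be randomized to the treatment or control (general health curriculum) conditions after baseline data collection". The study design has 3 ASPs per arm and 200 youth.

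**Interval.** Section B, Secondary Aims, item 3, puts the hypothesis that "changes in targeted social mechanisms will mediate the effects of the intervention on changes in PA affect, cognitions, and MVPA from baseline to post-intervention". The mediator is given no earlier interval.

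**Waves planned elsewhere.** For the social mechanisms, Primary Aim 2 states that "time (baseline to end of program and baseline to post-intervention) is a within subject factor". For PA, Study Measures says "Youth will wear an accelerometer over 7 consecutive days to calculate PA at baseline, endpoint, and post-intervention". For affect and cognitions, the analysis of Secondary Aims 1 and 2 gives only "time (baseline to post-) is a within subject factor". Figure 2 lists one block of post-measures per cohort.

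**The concern.** The first arm of any indirect effect here is the effect of the program on the mechanism. The program is assigned to ASPs, so that effect is known only to the precision that six sites allow. A bootstrap that resamples youth treats the 200 as independent. If youth in one ASP resemble each other, the interval for the indirect effect is too short and mediation is declared too often.

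The second issue is interpretation. With change in mechanism and change in PA taken over one interval, a model of arm to mechanism to PA and a model of arm to PA to mechanism fit equally well. Section B says that the trial will give preliminary information on social mediators to guide later intervention design, so a spurious or reversed mediator could carry forward into the larger trial.

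**Working it through.** The plan gives no ICC, effect size or power figure, so there is nothing to reproduce. Every ICC, effect and stability below is an assumption. From the documents: 200 youth, 6 ASPs, 3 per arm, hence m = 200/6 = 33.3 youth per ASP if sites are equal.

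**1. Size of the arm-to-mechanism test when ASP is ignored.** Design effect DE = 1 + (m - 1) x ICC; true size of a nominal 5% test = 2 x [1 - Phi(1.96/sqrt(DE))].

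| ICC of the change score | DE | 200/DE | True size |
|---|---|---|---|
| 0 | 1.00 | 200 | 5.0% |
| 0.02 | 1 + 32.33 x 0.02 = 1.65 | 121 | 12.7% |
| 0.05 | 1 + 32.33 x 0.05 = 2.62 | 76 | 22.6% |

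**2. Simulated rate of declared mediation.** Set-up: stability 0.55, residual SD 0.8, baseline correlation 0.3, one mechanism, no arm effect on it, mechanism-to-PA path 0.4, percentile 95% bootstrap over youth with 400 resamples. Repeated runs gave 5-6%, 11-12% and 16-18% at ICC 0, 0.02 and 0.05. With ASP accounted for, the rate was about 5% at each.

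These rates are below step 1 because the ICC here applies to the follow-up residual. The change score has variance 0.45² + 0.8² = 0.8425, of which 0.64 is residual. An ICC of 0.05 therefore becomes 0.05 x 0.64/0.8425 = 0.038, with DE 2.23 and size 18.9%. If the ICC is put directly on the change, simulation gives 22-24% at 0.05.

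**3. Power once ASP is accounted for.** At an assumed arm effect of 0.4, the SE of the arm difference in change is 2 x sqrt(0.8425 x DE/200) = 0.130, 0.159 and 0.194 at ICC 0, 0.02 and 0.05. The noncentrality 0.4/SE is 3.08, 2.52 and 2.06. Against the 4-df critical value 2.776, power for this path alone is 64%, 48% and 35%. Requiring the within-site mechanism-to-PA path as well, simulation gives 59%, 43% and 31%, against 82% for the unadjusted model with no clustering. ASP-adjusted power was not worked out for three mechanisms.

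**4. Direction, same-interval model, one mechanism measured without error, no clustering.** The range in each cell is over repeated runs.

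| Assumed effect | Declared under a purely reverse path | Declared under true mediation |
|---|---|---|
| 0.3 | 7-10% | 48-53% |
| 0.4 | 21-24% | 81-82% |
| 0.5 | 41-44% | 95-96% |

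The reverse-path rates move with the set-up. Over effects 0.3 to 0.5, three mechanisms (total effect) give 11-57%. At an assumed reliability of 0.8, one mechanism gives 2-20% and three give 4-34%.

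**5. What a lagged model adds and cannot do.** End-of-program mechanism to later PA, adjusted for baseline mechanism, baseline PA and end-of-program PA, calls the reverse path mediation in 0.4-2.7% of trials at effects 0.3-0.5 (one mechanism). At 0.4, without clustering, it detects mediation that continues after the program in 69% (one mechanism) or 40% (three, total effect). It detects mediation completed within the program in only 4-5%, against 80-81% for the same-interval model. With three mechanisms, at least one specific lagged effect is significant in 15% of trials when none exists.

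**6. Dates in Figure 2.** Cohort 3's program starts in January-March 2016 and its post-measures fall in April-May. Eight program weeks plus 12 weeks is 20 weeks, and 31 May 2016 less 140 days is 12 January. A program ending 31 March reaches 12 weeks on 23 June. For cohort 2, 31 December 2015 plus 84 days is 24 March 2016, inside its January-March block.

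**The case against.** **The aim is exploratory.** It is a secondary aim of a feasibility study, and no section says that it will establish direction. This stands, and it is why direction is the lesser point. A reader might infer that the plan claims to prove that social change comes first; the text does not. Nor is a significant same-interval result worthless: in step 4 it is roughly two to seven times as likely under true mediation as under the reverse path.

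**Clustering is a plan-wide gap.** This also stands. Section E mentions it for no aim. The mediation intervals still need it, and nothing elsewhere in the plan supplies it.

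**The resampling unit is unstated, so it might be the ASP.** That is possible, but nothing says so, and six sites are few for a site-level bootstrap.

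**The wave is less ambiguous than it looks.** Study Measures and Primary Aim 2 both separate the end of the program from post-intervention. Section B puts Secondary Aims 1 and 2 at 12 weeks, while section E gives the same aims as "trajectories (e.g., slight reduction; less increase) from baseline to post-intervention". The most consistent reading is that post-intervention means the 12-week wave. This stands, but Aim 3 still does not name the wave for the mediator.

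**Figure 2 is a coarse timeline.** A reader might infer that no cohort has both later waves. The blocks do not show that: cohort 2 could have end-of-program measures in early January and its 12-week measures by 24 March.

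**The lagged model has faults of its own.** It conditions on PA measured after randomisation and has little power for mediation completed in the program. Both are true, so it belongs beside the planned model and should not replace it.

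**Conclusion.** The analysis is wrong as written in one respect: indirect effects are to be bootstrapped without regard to the six randomised ASPs. With youth resampled as independent, the false declaration rate rises from about 5-6% to 11-12% at an ICC of 0.02 and 16-18% at 0.05. The exact size rests on assumed ICCs and on how the ICC enters the change score. At an ICC of zero there is no material inflation.

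The direction point is real but secondary. On the natural reading of one shared interval, a significant indirect effect supports the path without showing which change came first. The 7-44% range for a purely reverse path depends on assumed effects of 0.3-0.5, one mechanism and no measurement error. The documents support a stated limit and supplementary models, and do not support a charge that Aim 3 overclaims.

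**What to change.** **Main change.** Account for ASP in every mediation path. Test arm-to-mediator between sites on 6 - 2 = 4 degrees of freedom, estimate mediator-to-outcome within sites, and report each with its interval. This is analysis-plan wording; the price is the loss of power in step 3, which the plan should state.

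**Secondary changes.**
- Keep the planned model as exploratory, name the wave for each mediator and outcome, and state that it does not establish direction.
- Where the end-of-program and later waves are collected, add two supplementary lagged models: end-of-program mechanism to later PA, adjusted for baseline mechanism, baseline PA and end-of-program PA; and the reverse, with matching adjustments. Read the total indirect effect before the specific ones.
- State that the lagged model has little power for mediation completed within the program, that a null lagged result does not refute mediation, and that neither model removes confounding of mediator and outcome.
- Reconcile Figure 2 with the 12-week follow-up in Study Design, the accelerometer waves in Study Measures and the waves in section E. Say whether affect and cognitions are measured at end of program. Cohort 3 reaches 12 weeks by 31 May 2016 only if its program starts by about 12 January.

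**Cost if one cohort lacks a wave.** Four sites (about 133 youth) leave 2 degrees of freedom. At an effect of 0.4, adjusted for baseline, the SE is 2 x sqrt(0.64 x DE/133.3) = 0.139, 0.178 and 0.224 at ICC 0, 0.02 and 0.05, with DE as in step 1. Against the 2-df critical value 4.303, the arm-to-mediator path alone has about 37%, 25-26% and 18-19% power. The lagged result would then be descriptive only.

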Systematic observations will be conducted using the System for Observing Children's Activity and Relationships during Play (SOCARP; **see Appendix F**)^{73,74} and a modified version of the System for Observing Fitness Instruction Time (SOFIT) that includes a social climate observation tool that has been developed and tested by the PI (MCOT-PA).²⁹⁻³¹ Teams of two coders will make continuous observations of daily activities throughout 5 program days at each ASP. Observations will be used to assess changes in key social climate features for promoting youth affiliation goals. Staff structured interviews (**Readiness Assessment**) will assess staff perceptions of the feasibility and acceptability of the intervention program components conducted at baseline, mid-point, and post-intervention. This readiness assessment is developed to correspond with a multi-component theory of organizational readiness that addresses both program motivations and capacities⁷⁵ including motivation for implementing the CONNECT intervention, innovation-specific capacity for CONNECT, and general capacity, and has been previously piloted with principals, teachers, and technology specialists for a school-based technology intervention. We have adapted the assessment to fit within the afterschool program structure and PA goals of our intervention (**see Appendix H**).

The Social Motivational Orientations Scale for Sport (SMOSS)²³ will be used to assess changes in participants' degree of social affiliation orientation (7 items) and social validation orientation (8 items) toward PA (5-point scale, $M=2.44$; $SD=1.04$). The SMOSS is well-validated,^{23,76} correlated with PA value, enjoyment, and perceived ability, and has adequate internal consistency (reliability coefficients range from .77 to .87). **The Motivation for Physical Activities Measure (MPAM)** assesses five motives for participating in PA: Fitness, Appearance, Competence/Challenge, Social, Enjoyment. The scale has been used to predict various behavioral outcomes, such as attendance, persistence, or maintained participation in some sport or exercise activity, and to predict mental health and well-being and has demonstrated strong internal consistency (alphas above .87 for each of the subscales)⁷⁷ **The**

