PA Cognitions will be measured by **youth perceptions of their physical ability** (5-pt scale, $M=3.68$; $SD=.97$) and **value of PA** (5-pt scale, $M=3.81$; $SD=1.18$) using four items derived from the expectancy-value model that have been well-validated in youth minority populations⁹²⁻⁹⁴ (reliability coefficients range from .76 to .94). PA Affect will be measured by the extent to which adolescents engaged and enjoyed PA activities using **The Intrinsic Interest Scale**⁹⁵ (reliability coefficients from .83 to .94; 5-pt scale, $M=3.7$, $SD=1.0$) and the degree to which youth are concerned about performing well during PA using the worry subscale of **The Sport-Anxiety Scale-2** (reliability coefficient = .89; test-retest = .90; sum score range 4 to 20; $M= 12.12$; $SD=3.85$).⁹⁶ All PA cognition and affect measures have been shown to be correlated with the SMOSS and other measures of interest to the study (e.g., PA effort, ability).^{23,76,96} **Body Mass Index.** Height and weight will be measured at baseline and post intervention using a Shorr Height Measuring Board and a SECA 880 digital scale. Sex- and age-standardized BMI (zBMI) will be calculated for youth using CDC 2000 reference curves. (See Appendix G for Youth Survey measures).

Covariates. Demographic data will be collected on adolescents at baseline including self-report age (date of birth), race/ethnicity, and gender. Free /reduced lunch status will be derived from school/program records. The Positive Youth Development Scale (PYD-VSF; reliability coefficients from .72 to .90)⁹⁷ and The Strengths and Difficulties Questionnaire (SDQ; test-retest reliability=.80)^{98,99} will be used to measure indicators of positive development (e.g., connection, competence) and the presence of depressive symptoms because of previous research indicating an association between well-being/depression and youth PA and obesity. Lastly, the Self-Regulation Questionnaire- Prosocial (SRQ-Prosocial) assesses individual differences in prosocial behaviors, friendship, interpersonal skills, and exercise (reliability coefficients from .61-.85).¹⁰⁰

E. Analysis Plan

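### Secondary Aim 3 tests mediation of self-reported affect and cognitions on equal footing with accelerometer MVPA, although the mediators come from the same youth survey and shared reporting error can appear as mediation

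*Combined protocol and SAP*

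**What the plan says.** Section B, Secondary Aims, item 3: "Assess whether changes in targeted social mechanisms will mediate the effects of the intervention on changes in PA affect, cognitions, and MVPA", over the period from baseline to post-intervention. The three outcomes stand side by side.

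Section E, Secondary Aim 3, explores "whether changes in youth PA social orientations mediate the effect of the intervention on changes in adolescent PA outcomes". It plans a "multiple mediator model (estimated path model) where the indirect effect of the program on PA through social mechanisms will be examined", with bootstrapped total and specific indirect effects. It names no lead outcome and places no limit on how any indirect effect is read.

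Section D, Study Measures, shows where the variables come from:

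- **Mediators.** Aim 3 does not list them by scale. The measures matching the three targeted mechanisms are the SMOSS, which scores each youth's "degree of social affiliation orientation (7 items) and social validation orientation (8 items) toward PA"; the Need for Relatedness Scale; and the teacher-support and peer-climate scales, which "will be used to measure youth perceptions of staff and peer connections". The text refers to Appendix G for these.
- **Cognitions and affect.** Perceived ability, value of PA, intrinsic interest and worry are youth self-reports, also referred to Appendix G. The protocol adds: "All PA cognition and affect measures have been shown to be correlated with the SMOSS and other measures of interest to the study".
- **MVPA.** "Objective assessments of PA will be obtained on youth with omni-directional accelerometers".

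Blinding is described for measurement staff only.

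**The concern.** Randomisation protects the path from arm to mediator. It does not protect the path from mediator to outcome, because nobody is randomised to a level of affiliation or relatedness. When the same youth reports both ends of that path in one survey, mood, response style or a wish to please can move both scores together. The path model reads that shared movement as an effect of the mediator on the outcome.

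Nothing in the plan removes this. The bootstrap describes sampling error, not bias. The covariates listed for the other aims are demographics, BMI and variables that differ by arm at baseline; they do not capture error shared by two changes. No method factor, correlated-error term or separation of mediator and outcome in time is specified. The youth who report know which programme they attend, so part of an arm difference on the mediators could itself be reporting.

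The trial's theory is that social mechanisms carry the effect on PA, and its results are to inform a larger efficacy trial. An indirect effect on enjoyment or value, reported level with one on MVPA, could carry a same-survey association forward as evidence of mechanism.

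**Working it through.** The documents give no alpha, power or effect size for Aim 3, so there is no planned figure to reproduce. The check is a simulation for illustration.

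**Inputs from the documents.** 200 youth in year 2, taken as 100 per arm.

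**Assumed inputs.** Arm effect on the reported mediator, a = 0.1 to 0.4 SD; correlation of mediator and outcome change from shared reporting error, r = 0 to 0.3; within-arm SD of 1; one mediator; clustering by ASP ignored.

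**Model.** M = a·T + e1 and Y = e2, with corr(e1, e2) = r and no effect of M on Y. The true indirect effect is zero. The fitted mediator-to-outcome coefficient centres on r, so the apparent indirect effect centres on a × r; for example 0.4 × 0.2 = 0.08.

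**How often the 95% interval for the indirect effect excludes zero:**

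| Arm effect on mediator | r = 0 | r = 0.1 | r = 0.2 | r = 0.3 |
|---|---|---|---|---|
| 0.1 SD | 0% | 2% | 8% | 13% |
| 0.2 SD | 0% | 5% | 21% | 28% |
| 0.3 SD | 3% | 14% | 43% | 56% |
| 0.4 SD | 4% | 22% | 62% | 78% |

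The lower two rows use 3,000 trials per cell and the upper two 1,200, with a Monte Carlo interval. A repeat of the 0.4 SD row gave 4%, 22%, 63% and 80%, so the last cell is about 79%.

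**Hand check.** An indirect effect is significant roughly when both of its paths are.

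- SE(a) = √(2/100) = 0.141. For a = 0.4, z = 2.83 and the power is Φ(2.83 − 1.96) ≈ 0.81.
- SE(b) ≈ √((1 − r²)/197). For r = 0.2 this is 0.070, so z = 2.87 and the power is ≈ 0.82. Product: 0.81 × 0.82 ≈ 0.66 (simulated 62%).
- For r = 0.3, SE(b) = 0.068, z = 4.41 and the power is ≈ 0.99. Product ≈ 0.80 (simulated 78%).
- For r = 0, 0.81 × 0.05 ≈ 0.04 (simulated 4%).
- For a = 0.1 and r = 0.1, 0.105 × 0.29 ≈ 0.03 (simulated 2%).

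**Percentile bootstrap, the kind of interval planned (600 trials per setting).** At 0.3 SD, the rates for shared-error shares of 0, 5, 10, 20 and 30% of change variance were 3, 7, 16, 42 and 56%. When the 0.3 SD difference lay only in reporting, they were 3, 7, 14, 43 and 57%. With no arm difference on the reported mediator, the rate stayed at or below about 5%. An outcome free of the shared error, such as a device measure, stayed at about 2–6% when the arm effect was 0.3 or 0.5 SD.

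**Several mediators.** With three mediators intercorrelated at 0.5 (assumed), 0.4 SD and r = 0.2, two runs gave a false-positive rate of about 69–71% for the total indirect effect and about 15–17% for any one specific effect. At least one of the three specific effects was significant in about 42%.

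**Can the documents fix r?** No. The stated SMOSS reliability of .77 to .87 leaves 1 − .87 = 13% to 1 − .77 = 23% error variance at one time point, but nothing says how much error is shared with the outcome scales. Internal consistency does not bound it either, since a response style that runs through all items counts as reliable variance.

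**The case against.** Several points on the other side stand.

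- **Any movement of the mediators.** A reader might infer that false mediation becomes likely as soon as Connect shifts the mediator scales at all. The table does not support that: at 0.1 to 0.2 SD the rates are about 2% to 28% for r = 0.1 to 0.3. They pass one half only at 0.4 SD with r of 0.2 or more, or at 0.3 SD with r = 0.3.
- **The stated correlation with the SMOSS.** It is tempting to read this as an admission of shared error. It is a validity statement about scale scores, and a real mechanism would also produce it.
- **One direction of bias.** Worry is a sum score on which higher presumably means more worry. Yes-saying would tie it positively to affiliation and could mask mediation, while a wish to make a good impression would inflate it.
- **Timing and change scores.** The plan does not say whether changes are differences or baseline-adjusted scores. The mechanisms are analysed at two later time points, so a lagged model is possible. Appendix G itself is not in the text, so completion in one sitting is an inference.
- **Priority elsewhere.** Section B speaks of preliminary data on social mediators for improving MVPA, and the Section E wording on the programme's effect on PA could mean MVPA alone. That leans towards MVPA, but item 3 of the Secondary Aims still lists all three outcomes level, so the two sections need aligning in any case.
- **Standing of the aim.** Aim 3 is exploratory, in a feasibility study, with no decision rule attached. This lowers the stakes but does not remove the bias.

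**Conclusion.** The point holds as a limit on interpretation. The mediators and the affect and cognition outcomes share a source, MVPA does not, and the plan treats them alike. The bias in the mediator-to-outcome path is structural. Its size is unknown: about 2% to 79% false positives over the assumed grid with shared error present, against about 4% or less without it. These figures rest on one mediator, 100 independent youth per arm, and assumed values of both a and r. In a multiple-mediator model the total indirect effect is affected more than any single specific effect.

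Two further inferences go too far. The documents do not support discarding mediation of affect and cognitions, which are named Aim 3 outcomes and can only be self-reported. Nor does a device outcome make mediation of MVPA secure: it removes same-source error only, and ordinary confounding of mediator and outcome remains.

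**What to change.** In Section E, Secondary Aim 3:

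1. Name accelerometer MVPA as the lead mediation outcome, with the total indirect effect first and the specific effects after it. Bring item 3 of the Secondary Aims in Section B into line.
2. Keep the mediation analyses of affect and cognitions as supportive. State that mediators and outcomes come from the same youth survey, that part of any indirect effect may be shared reporting, and that for worry the direction of bias may differ.
3. Add a sensitivity analysis for the self-reported outcomes that allows correlated mediator-outcome error. The residual correlation cannot be estimated alongside the mediator-to-outcome path, so fix it at a few values (for example 0.1, 0.2 and 0.3) and report the value at which the interval for the indirect effect first includes zero.

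The data and main models do not change. The cost is a few sentences, slightly more analysis, and a weaker mediation claim for affect and cognitions. The text should also say that mediation of MVPA remains subject to ordinary mediator-outcome confounding.
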